adjusted. Subjects who are ≥ 60 kg of body weight at consent and drop below that body weight will receive 45 mg dose at any subsequent visit. Subjects ≥ 30 and < 60 kg at consent increasing their weight to ≥ 60 kg will increase their dose to 60 mg.

^c Edoxaban dosage regimen will be reduced permanently for subject with body weight <5th percentile for age. Refer to Appendix 17.11.

^d Per Principal Investigator's discretion, for subjects in Cohort 2 that require either 45 mg or 60 mg dose, the Principal Investigator may use edoxaban tablets instead of granules, if they wish.

^e Edoxaban granulation will be diluted with 8 mL water to provide a concentration of 6 mg/mL dosing suspension. If body weight increases or decreases from the categories of weight defined at consent, the subject will be dose adjusted. Subjects who are ≥60 kg of body weight at consent and drop below that body weight will receive 45 mg dose at any subsequent visit. Subjects ≥30 and <60 kg at consent increasing their weight to ≥60 kg will increase their dose to 60 mg.

Note: Dose is based upon weight at corresponding visit.

For subjects without prior anticoagulant therapy, edoxaban may be started the day of randomization (Day 1).

Proprietary and Confidential Page 55 For subjects who received VKA treatment prior to randomization and are randomized to edoxaban, VKA treatment will be discontinued the day before randomization and edoxaban dose will be initiated when an INR \leq 2.5 is reached.

5.1.1.2. Standard of Care Treatment Arm (Randomization to Month 3).

SOC randomized subjects will be treated with SOC though Month 3 (Visit 5) and then offered edoxaban through Month 12. SOC treatment will be packaged and dispensed to the subject on a monthly visit schedule. After Month 3, all subjects will be transitioned to edoxaban at the appropriate dose for their age and weight. Locally sourced SOC is the preferred option for this study, either by the Investigator or, alternatively local supply depots within each country that provide SOC directly to the clinical sites. However, centrally sourced SOC can be provided when the country or clinical site requirements deem it necessary. In the case of centrally sourced treatment, the Sponsor will only provide enoxaparin as LMWH and warfarin as VKA.

For subjects who did not receive VKA treatment prior to randomization and are randomized to SOC with VKA, VKA treatment may be started on the day of randomization (Day 1).

It is the Investigator's discretion based on his/her local practice and on the subject's underlying cardiac disease to consider if heparin bridging is necessary when initiating VKA post randomization until an INR between 2.0 and 3.0 is reached. Heparin bridging will be provided by the Investigator.

5.1.2. Method of Treatment Allocation

Eligible subjects will be stratified as mentioned in Section 5.1.1. An independent biostatistician will generate the randomization schedule in accordance with the operating procedure for allocating study drug.

At randomization, the Investigator provides the Interactive Web/Voice Response System (IXRS) with the clinical site number and the subject's presenting diagnosis and date of birth.

Dose will be reduced for subjects based on the following criteria:

- eGFR is 30-50% of normal for age and size (Appendix 17.9). If a subject experiences a change in renal function from normal to eGFR \geq 30% to \leq 50% after randomization, the measurement will be repeated within 1 week. If the repeat measurement confirms the eGFR \geq 30% to \leq 50%, the edoxaban dose will be reduced permanently.
- Subject is receiving concomitant treatment with P-gp inhibitors. The dose will be reduced while on P-gp inhibitor and re-established to original dose once the concomitant medication is stopped (Appendix 17.6.1).
- Body Weight:

For subjects 12 to <18 years old with body weight $<5^{th}$ percentile of subject's age (see Appendix 17.11), edoxaban doses will be permanently changed.

For subjects 12 to <18 years old with body weight ≥ 60 kg, will receive edoxaban 60 mg. However, if the body weight is $\geq 30 - <60$ kg, edoxaban dose would be 45 mg daily. If the patient body weight ≥ 60 kg, then edoxaban dose would be escalated to 60 mg daily.

Proprietary and Confidential Page 56 For subjects <12 years old: Doses will be provided by mg/kg or a dose may be suggested, subsequent to exposure modeling, based on an age range (see Table 5.1).

The IXRS will assign the unique subject identification number, allocate the treatment group assignment for the subject and provide the appropriate drug supply kit number(s).

A fax or e-mail will be sent by the IXRS to provide the appropriate drug supply kit number(s). The fax or e-mail will also provide a calendar with dates of subsequent prescheduled visits and drug resupply.

5.1.3. Blinding

Not applicable.

5.1.4. Emergency Unblinding Procedure

Not applicable.

5.2. Study Drug(s)

5.2.1. Description

The study drug for this study is edoxaban (DU-176b) and SOC anticoagulants (UFH/LMWH and VKA). The active ingredient is edoxaban tosylate and the international non-proprietary name is N-(5-Chloropyridin-2-yl)-N'-[(1S,2R,4S)-4-(N,N-dimethylcarbamoyl)-2-(5-methyl-4,5,6,7-tetrahydro[1,3]thiazolo[5,4-c]pyridine-2-carboxamido)cyclohexyl] oxamide mono (4-methylbenzenesulfonate) monohydrate.

5.2.1.1. Edoxaban (Randomization through Month 12)

Edoxaban will be packaged and supplied to the subject on a monthly visit schedule as tablets (15 and/or 30 mg strength) or granules for oral suspension (60 mg strength) even though after Month 3 the clinic visitation schedule is every 3 months. For subjects who cannot pick up their study therapy on a monthly basis, accommodations will be made to allow the Investigator to distribute up to a 3-month supply of study drug to match the scheduled study visit interval.

Subjects will be instructed to take edoxaban (tablets or granules) orally once a day, at the same time every day, preferably in the morning, with or without food. One bottle of edoxaban granules will be used for each dosing day. Tablets should be swallowed with a glass of water.

The doses will be dispensed as follows:

For subjects 12 to <18 years old:

- A 60 mg dose will be dispensed as two 30 mg tablets or 10 mL from an individual bottle of oral suspension 60 mg
- A 45 mg dose will be dispensed as one 30 mg tablet plus one 15 mg tablet or 7.5 mL from an individual bottle of oral suspension 60 mg

- A 30 mg dose will be dispensed as one 30 mg tablet or 5 mL from an individual bottle of oral suspension 60 mg
- Doses provided by the granulation formulation will be dispensed with a dosing syringe according to the recommended dose shown in Table 5.1.
- If a subject does not have the capacity to swallow tablets in the 12 to <18 year and 6 to <12 year old groups, the tablets may be crushed and served with applesauce or mixed with 2 to 3 ounces of water and immediately administered by mouth or through an existing gastric tube, if needed.

For subjects 6 to <12 years old:

- 60 mg dose will be dispensed as two 30 mg tablets or as 10 mL from an individual bottle of oral suspension 60 mg.
- 45 mg dose will be dispensed as one 30 mg tablet plus one 15 mg tablet or as 7.5 mL from an individual bottle of oral suspension 60 mg.
- Dose other than 45mg and 60mg provided by the granulation formulation will be dispensed with a dosing syringe according to the recommended dose shown in Table 5.1. One bottle will be used for each daily dose.

5.2.1.2. Standard of Care (Randomization through Month 3)

Treatment with SOC will only occur through Month 3. After that time all subjects will be offered edoxaban at a dose appropriate for age and weight. Local sourcing will be the preferred option for SOC drugs, either by the Investigator or local depot providing locally utilized therapy to treat TE. The Sponsor will supply central sourcing as an alternative option to local SOC sourcing.

Clinical supply will be packaged and dispensed to the subject on a monthly visit schedule.

If local sourcing is used, the Investigator is allowed to utilize any UFH or LMWH, and/or VKA according to the SOC treatment specific to that clinical site (no strength restrictions).

If central sourcing is used, only enoxaparin and warfarin will be supplied by the Sponsor at fixed doses as the LMWH and the VKA, respectively. If a subject is prescribed a dose of the LMWH or VKA different from the doses supplied, a combination of the various doses should be used to obtain the desired dose. Guidance on dosing and dispensing is provided in Appendix 17.2.

Note: If standard practice for bridging VKA to therapeutic levels is achieved with a heparin (UFH or LMWH) based treatment, the clinical site will be responsible for providing the bridging therapy for subjects randomized to VKA.

If required, the Sponsor will provide centrally sourced SOC treatment at the following fixed doses:

- Enoxaparin (LMWH) will be provided as solution for SC injection in pre-filled syringes with only 60 mg/0.6 mL, 80 mg/0.8 mL, and 100 mg/1.0 mL concentration for injection, or as multiple dose vials (for subjects <20 kg).
- Warfarin (VKA) will be supplied as tablets (0.5 mg, 1 mg, and 3 mg). Various doses will be available for INR maintenance in the therapeutic range of 2 to 3.

5.2.1.3. Aspirin

Clinical sites or treating physicians will provide aspirin (as per local SOC practice).

5.2.2. Labeling and Packaging

5.2.2.1. Edoxaban

Study drug will be provided in adequate quantity for study conduct and labeled in an open-label format. Study drug labels will include all information required by federal and local regulations.

Edoxaban 15 and 30 mg tablets will be supplied by the Sponsor in an open-label format. The edoxaban 60 mg granules for oral suspension will be provided in glass bottles, as per visit schedule, for single dose administration.

5.2.2.2. Standard of Care

Standard of care sourced locally either by the Investigator or by a local depot providing SOC to the clinical site will have no modification in labeling or packaging. Hence, locally sourced SOC treatment will have a label identical to the procured drug.

If required, centrally sourced SOC treatment will be presented in its commercial presentation with the clinical study over-label. SOC labels will include all information required by federal and local regulations.

Note: If standard practice for bridging VKA to therapeutic levels is achieved with a heparin based treatment, the clinical site will be responsible for providing the bridging therapy if the subject is randomized to VKA.

5.2.3. Preparation

5.2.3.1. Edoxaban

No special preparation will be required for the tablet formulation. However, if a subject does not have the capacity to swallow tablets in the 12 to <18 year old group, the tablets may be crushed and served with applesauce or mixed with 2 to 3 ounces of water and immediately administered by mouth or through an existing gastric tube, if needed.

The edoxaban granules for oral suspension 60 mg will be provided in amber glass bottles (wide neck) with child-resistant caps. The edoxaban granules for oral suspension 60 mg formulation will be reconstituted with 8 mL of water to provide a 6 mg/mL liquid suspension. One bottle will be used for each daily dose. Instructions for reconstitution will be provided to the Investigator/designee and the caregiver.

5.2.3.2. Standard of Care

No special preparation will be required for locally (or centrally) sourced SOC. Instructions for daily use will be provided to the Investigator/designee.

5.2.4. Administration

Study drug will be packaged and dispensed to the subject on a monthly visit schedule. For subjects who cannot pick up their study therapy on a monthly basis, accommodations will be made to allow the Investigator to distribute up to a 3-month edoxaban supply of study drug (for those continuing after Month 3 through Month 12) to match the scheduled study visit interval. Note that each monthly dispensing visit is not indicated in Table 17.1 because no additional procedures are expected at the monthly dispensing visits.

Locally sourced study drug will be provided by the Investigator or through a depot within the country of the clinical site. If required, centrally sourced study drug will be shipped to the clinical sites, and the Investigator/designee will be responsible for dispensing the study drugs. The Investigator/designee will provide the subjects with product in sufficient quantity, plus overage, via IXRS dispensing until the next scheduled visit.

The Investigator/designee will also instruct the subject on reporting study drug or SOC administration and accountability. Subjects who miss 1 dose of study drug or SOC will be instructed to skip that dose and take the next dose at their drug administration schedule.

5.2.4.1. To Initiate Edoxaban Treatment at Randomization

For subjects without prior anticoagulant therapy, edoxaban may be started the day of randomization (Day 1).

For subjects who received VKA treatment prior to randomization and are randomized to edoxaban, VKA treatment will be discontinued the day before randomization and edoxaban dose will be initiated when an INR \leq 2.5 is reached. It is per Investigator's discretion based on his/her local practice and on the subject's underlying cardiac disease to consider if heparin bridging is necessary during this period. Heparin bridging will be provided by the Investigator.

If heparin bridging is used, edoxaban will be started as below:

- 1. In case of bridging with a LMWH twice a day regimen, edoxaban dosing will start 12 ± 3 hours after the last LMWH dose
- 2. In case of bridging with a LMWH once a day regimen, edoxaban dosing will start 24 ± 3 hours after the last LMWH
- 3. In case of bridging with a UFH regimen, edoxaban dosing will start 4 ± 1 hour after the last UFH dose

5.2.4.2 Transition SOC-Treated Subjects during the Main Treatment Period to Edoxaban in the Extension Period

For subjects who received VKA treatment edoxaban dosing will be initiated when an INR \leq 2.5 is reached. This may occur as early as next day of the Extension Period.

If the subject was originally randomized to UFH or LMWH, edoxaban will be started as below:

1. In case of LMWH twice a day regimen, edoxaban dosing will start 12 ± 3 hours after the last LMWH dose

- 2. In case of LMWH once a day regimen, edoxaban dosing will start 24 ± 3 hours after the last LMWH
- 3. In case of UFH regimen, edoxaban dosing will start 4 ± 1 hour after the last UFH dose

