5.2.4.3 To Initiate SOC Treatment

If the subject is randomized to the SOC treatment and they use locally sourced SOC, they will receive the following SOC anticoagulant treatment according to the clinical site's usual treatment practice (alone or in combination):

- LMWH (alone or with VKA)
- UFH (alone or with VKA)
- VKA (alone or with LMWH or UFH)

For subjects who do not receive VKA treatment prior to randomization and are randomized to SOC with VKA, VKA treatment may be started on the day of randomization (Day 1).

It is per Investigator's discretion based on his/her local practice and on the subject's underlying cardiac disease to consider if heparin bridging is necessary post-randomization until an INR between 2.0 and 3.0 is reached. Heparin bridging will be provided by the Investigator.

If centrally sourced SOC treatment is required from the Sponsor, the subject will be treated as follows:

- For subjects randomized to enoxaparin: Neonates or children receiving either once- or twice-daily therapeutic enoxaparin should be monitored as per local practice.
- For subjects randomized to warfarin, it is recommended that the dose should be titrated to achieve a target INR of 2.0 to 3.0. It is per Investigator's discretion based on his/her local practice and on the subject's underlying cardiac disease to consider if heparin bridging is necessary during this period. Visits will be at the discretion of the Investigator and captured as unscheduled visits for data collection. Adjustment of the maintenance dose of VKA will be dependent on INR monitoring as follows:
 - INR 2.0 to 3.0, no change in dose
 - INR 1.1 to 1.4, increase dose by 20%
 - INR 1.5 to 1.9, increase dose by 10%
 - INR 3.1 to 3.5, decrease dose by 10%

INR >3.5, hold VKA until INR is <3.5, then decrease dose by 20% when restarted.

To initiate SOC post screening, it is recommended to test infants and children every 4 weeks once a stable dose of VKA has been achieved. However, depending on the site's clinical practice and PI's discretion, the subjects can be tested at the physician's discretion and/or according to local practice. More frequent INR testing is recommended in infants and children receiving VKA with any change in diet or medication or when an illness occurs. An unscheduled visit will need

to be performed to document the discretionary INR measurement and potential VKA dosage change as an unscheduled visit day.

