11.4.3. Safety Analysis

11.4.3.1. Analysis of Bleeding Events

The primary safety endpoint is the composite of major and CRNM bleeding events that occur during the Main Treatment Period: from the date of first dose of study drug to the Month 3 Visit, or to the date of last dose of study drug plus 3 days if study treatment is discontinued, whichever is earlier. This analysis will be based on CEC adjudication results.

The time to major or CRNM bleeding occurring during the Main Treatment Period will be compared between treatment groups for subjects in the Safety Analysis Set, using the Cox proportional hazards regression model with treatment group, concomitant usage of aspirin at baseline, and underlying disease (Kawasaki disease, Fontan surgery, heart failure or Other) as covariates. Hazard ratio between edoxaban and SOC treatment group will be calculated with corresponding 95% CI. The incidence, annualized event rate, and rate difference between edoxaban and SOC treatment groups will also be calculated.

In addition, incidence, annualized event rate and rate difference between edoxaban and SOC treatment groups with corresponding 95% CI will be calculated for following endpoints for Safety Analysis Set for the Main Treatment Period. Incidence and annualized event rate will also be calculated for the following endpoints occurring from the day after Month 3 Visit to date of last dose of study drug plus 30 days in the Extension Period.

- Major and CRNM bleeding event combined
- Major bleeding event
- All bleeding event (major, CRNM, and minor bleeding combined)

The above 3 categories of bleeding endpoints will also be summarized for the periods and subjects below:
- Incidence, annualized event rate, and rate difference will be calculated for events occurring from the date of first dose of study drug to the date of last dose of study drug plus 30 days for subjects who do not participate in the Extension Period.
- Incidence and annualized event rate will be calculated for events occurring from the day after Month 3 Visit to the data of last dose of study drug for subjects who participate in the Extension Period.

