17.4. Contraindications for Standard of Care Therapy

Contraindications to warfarin (COUMADIN):

- Hypersensitivity to the active substance or to any of the excipients
- Hemorrhagic stroke
- Clinically significant bleeding
- Use within 72 hours of major surgery with risk of severe bleeding
- Use within 48 hours postpartum
- Pregnancy
- Drugs where interactions may lead to a significantly increased risk of bleeding

Contraindications to enoxaparin (LOVENOX):

- Hypersensitivity to either enoxaparin sodium, heparin or its derivatives including other LMWH
- Acute bacterial endocarditis
- Active major bleeding
- Conditions with a high risk of uncontrolled hemorrhage, including recent hemorrhagic stroke or thrombocytopenia in subjects with a positive in-vitro aggregation test in the presence of enoxaparin; active gastric or duodenal ulceration
- Subjects receiving heparin for treatment rather than prophylaxis

Note: Loco-regional anesthesia in elective surgical procedures is contraindicated.

Contraindications to UFH:

- History of heparin-induced thrombocytopenia (with or without thrombosis)
- Uncontrolled, active bleeding (except disseminated intravascular coagulation)
- Acute bacterial endocarditis
- When suitable, blood-coagulation tests (eg, the whole-blood clotting time, partial thromboplastin time, etc) cannot be performed at appropriate intervals
- Hypersensitivity to heparin
- Advanced renal or hepatic dysfunction
- Severe hypertension
- Major surgery involving the brain, spinal cord and eye.

17.5. Prohibited Concomitant Medications at Any Time during the Treatment Period with Edoxaban or SOC

The list here (in the protocol) is static and reflects the list at the time of the current version of the protocol. If there are changes to this list during the study, the changes will not be considered a protocol amendment and the list in this appendix will not be updated unless the protocol is being amended for other reasons as well.

Subjects on these drugs at the time of planned randomization will be excluded from the study. After randomization, use of these drugs will require a study drug permanent discontinuation unless advised otherwise in the Sections below. The Investigator is encouraged to contact the Medical Monitor for further guidance.

Sites will receive a contact card where the following numbers (24-hour Urgent Medical Contact) are provided:

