17.5.3. Parenteral Anticoagulants

Parenteral anticoagulants are prohibited in the edoxaban-treatment arm. Direct thrombin inhibitors are prohibited in both the edoxaban arm and in the SOC arm.

Examples of prohibited parenteral anticoagulant medications include the following:

- LMWH: enoxaparin (Lovenox®, Clexane®), dalteparin (Fragmin®), tinzaparin (Innohep®, Logiparin®), reviparin (Clivarin®), nadroparin (Fraxiparine®), ardeparin (Normiflo®), certoparin (Sandoparin®), parnaparin (Fluxum®)
- UFH: Calciparine®
- Direct thrombin inhibitors: bivalirudin (Angiomax®), argatroban, (Acova®), desirudin (Iprivask®), lepirudin (Refludan®)
- FXa inhibitors: fondaparinux (Arixtra®)

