17.7. Transition From Edoxaban to Other Anticoagulants

Subjects who require anticoagulation at the end of study participation will be transitioned to standard-of-care treatment as directed by the Investigator or treating physician.

At the end of edoxaban treatment, the subject will receive the last dose of edoxaban and all remaining edoxaban tablets/bottles will be collected from the subject by site staff.

Subjects transitioning from edoxaban to any VKA will have their INR recorded at last study visit. Bridging with heparin may occur during VKA titration until the INR is at a therapeutic level of 2 to 3.

INR will need to be measured as frequently as necessary until the INR target of ≥ 2 . Once the INR is ≥ 2.0 the heparin will be stopped and the subject will continue on the VKA alone.

When transitioning from edoxaban to another direct oral anticoagulant (e.g. rivaroxaban, apixaban, dabigatran):

• The first dose of the direct oral anticoagulant of choice will be given 24 hours post the last dose of edoxaban and will then be continued as per the novel anticoagulant's label.

For subjects who do not complete the Main Treatment Period, they will be followed with monthly visits until the end of Month 3 and have a 30-day Follow-Up Visit according to the Schedule of Events (Appendix 17.1).

For subjects who complete the Main Treatment Period but do not continue into the Extension Treatment Period, the subjects will receive a Discontinuation Visit and a Follow-Up Visit, 30 days after last dose of study drug.

For subjects who continue into the Extension Period, the Follow-Up Visit will occur 30 days after the Discontinuation Visit (Month 12, Visit 8).

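### Section 5.2.4.1 permits heparin bridging after randomization in the edoxaban arm, which Section 5.5 and Appendices 17.5 and 17.5.3 forbid without exception, and the start of the primary bleeding window is undefined for a bridged child

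*Combined protocol and SAP*

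**What the plan says.** Starting edoxaban. For VKA-pretreated children in the edoxaban arm, Section 5.2.4.1 provides that "VKA treatment will be discontinued the day before randomization and edoxaban dose will be initiated when an INR" of 2.5 or lower is reached. The investigator is "to consider if heparin bridging is necessary during this period". The section then gives separate intervals from last heparin to first edoxaban for twice-daily LMWH, once-daily LMWH and UFH. No INR level is set for giving the heparin.

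The prohibition. Appendix 17.5.3 states: "Parenteral anticoagulants are prohibited in the edoxaban-treatment arm", and its list of examples includes LMWH and UFH. Appendix 17.5 gives the consequence: "After randomization, use of these drugs will require a study drug permanent discontinuation unless advised otherwise in the Sections below". Section 5.5 bars anticoagulants other than the assigned study drug by any route and says study drug should be discontinued.

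Bridging elsewhere. For the SOC arm, Section 5.1.1.2 asks the investigator "to consider if heparin bridging is necessary when initiating VKA post randomization until an INR between 2.0 and 3.0 is reached", and Section 5.2.4.3 repeats this. In Appendix 17.7, for the move from edoxaban to a VKA, once INR is at least 2.0 "the heparin will be stopped and the subject will continue on the VKA alone". Section 5.2.4.2, on the Month 3 switch from VKA to edoxaban, does not mention bridging.

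The bleeding window. Section 11.4.3.1 counts the primary composite "from the date of first dose of study drug to the Month 3 Visit", or to 3 days after the last dose if treatment is discontinued and that is earlier. Section 2.3.2 opens the all-bleeding endpoint at the same point. Section 2.3.3 counts thromboembolic events and mortality from randomization.

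**The concern.** There are two separate problems.

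The first is operational. A site that bridges under Section 5.2.4.1 would, on the wording of Section 5.5 and Appendix 17.5, have to stop study drug in a child it was told it could bridge. Sites may resolve this differently. That would affect which children are bridged, which are discontinued, and what is recorded as a deviation.

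The second is about counting. The primary endpoint depends on when first dose occurs, and for a bridged child in the edoxaban arm the protocol supports two answers. If the clock starts at first edoxaban, bleeds between randomization and that dose fall outside the primary and all-bleeding endpoints. In the SOC arm heparin and VKA are themselves study drug, so bleeds during bridging can be counted.

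**Working it through.** **1. Does the permission collide with the prohibition?**

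- Permission: Section 5.2.4.1. The three heparin-to-edoxaban intervals show that heparin after randomization is intended.
- Prohibition: Section 5.5 and Appendix 17.5.3.
- Timing: Appendix 17.5 applies after randomization, and Section 6.4 starts the Main Treatment Period at randomization.
- Exceptions: Appendix 17.5 allows them only where its own subsections say so. Appendix 17.5.3 has none for bridging, and neither has Section 5.5.

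The passages cannot all be followed.

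**2. At what INR may heparin be given?** The period runs from VKA stop to first edoxaban. It therefore includes any time spent waiting for INR to fall to 2.5, and nothing excludes heparin during that time. INR need not be above 2.5 for the whole period: Section 5.1.1 expects some VKA-pretreated children to be at or below 2.5 and dosed on Day 1.

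**3. When does the primary clock start for a bridged child?**

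- Section 5.2.1 names UFH/LMWH and VKA, together with edoxaban, as study drug and does not restrict this by arm. On that reading a bridging dose could start the clock.
- Section 3.3 describes the primary endpoint in subjects given at least one dose of randomized study drug. On that reading only edoxaban starts it.
- Section 11.2 admits a child to the Safety Analysis Set on one dose of study drug and analyses by drug actually received. On the first reading, a child who received only bridging heparin could enter the set and be analysed as SOC.

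**4. The plan's own figure.** Section 11.6 assumes 8.5% and 10.3% with 100 and 50 subjects. The difference is 0.085 − 0.103 = −0.018. The unpooled SE is √(0.085×0.915/100 + 0.103×0.897/50) = 0.0512. Then −0.018 ± 1.96×0.0512 gives −11.8% to 8.2%, as stated.

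**5. How many bleeds could go uncounted if only edoxaban starts the clock?** The documents do not give the number of children waiting, the length of the wait, or the period to which 8.5% refers. Assumed: 20 to 50 of 100 children, 1 to 5 days, and 8.5% as a 90-day risk with constant hazard.

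- Hazard: −ln(1 − 0.085)/90 = 0.00099 per day.
- Person-days: 20×1 = 20 to 50×5 = 250.
- Expected bleeds: 0.00099×20 = 0.02 to 0.00099×250 = 0.25.
- With a 1-day wait only: 20 to 50 person-days, or 0.02 to 0.05.
- If the overlap multiplied risk fivefold (a further assumption), 50 children waiting 5 days would give 50×0.085×(5/90)×5 = 1.2. With a 2-day wait this is 0.47.

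**6. What would one bleed do?** Adding one to the edoxaban arm raises 8.5% to 9.5%. The difference moves from −1.8 to −0.8 points, with a 95% CI of −11.0% to 9.4%.

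**The case against.** The strongest reply is that Section 5.2.4.1 is the specific rule and overrides the general ban. Appendix 17.5 is headed as applying to the treatment period with edoxaban or SOC, and edoxaban has not yet been given during bridging. The intent to permit bridging is indeed plain. But the operative sentence in Appendix 17.5 runs from randomization and admits exceptions only from its own subsections, so the written conflict stands.

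A reader might infer that Section 5.2.4.1 directly contradicts the protocol's heparin-stop level. The documents do not support that. The limits in Sections 5.1.1.2 and 5.2.4.3 and in Appendix 17.7 are written for starting a VKA, whereas here a VKA is being stopped. Nor does silence in Section 5.2.4.2 forbid bridging. What remains is an unexplained difference between transitions.

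A reader might also infer that these bleeds certainly escape the primary endpoint and bias it toward edoxaban. That is not established, because Section 5.2.1 can be read to start the clock at the bridging dose in either arm. Opening bleeding at first dose and thromboembolism at randomization is an explicit choice and not in itself an error. A bleed on VKA plus heparin before any edoxaban is also not evidence about edoxaban.

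Finally, Section 6.3 places the first dose on Day 1 or Day 2, which suggests that the wait is usually short. That is fair, although the INR condition itself has no time limit.

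**Conclusion.** The conflict between Section 5.2.4.1 and Section 5.5, Appendix 17.5 and Appendix 17.5.3 is in the text and needs correcting. This conclusion depends on no assumed number. It matters because the instructions concern anticoagulation in children and one of them ends study treatment.

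The counting point is an undefined term with a small expected effect: about 0.02 to 0.25 bleeds under the stated assumptions, and near the lower end if the wait is 1 or 2 days. An asymmetry between the arms arises only if first dose means first edoxaban. One bleed is 1.0 point in an arm of 100, in an unpowered descriptive study whose planned interval is about 20 points wide. This is a reason to define the term and show a supplementary count. It does not show that the primary comparison is materially biased.

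**What to change.** 1. Reconcile Section 5.2.4.1 with Section 5.5, Appendix 17.5 and Appendix 17.5.3, and explain why the INR conditions for heparin differ from those in Sections 5.1.1.2 and 5.2.4.3 and Appendix 17.7. The clinical rule is for the sponsor's clinicians to decide.
2. Define first dose of study drug in the edoxaban arm, both for the primary endpoint and for entry to the Safety Analysis Set.
3. In Section 11.4.3.1, add a supplementary analysis of adjudicated major plus CRNM bleeding from randomization in both arms. Add a listing of bleeds between randomization and first edoxaban dose, showing heparin given and INR where measured.

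Cost: wording changes, one table and one listing. Adverse events are recorded from consent (Section 9.2) and suspected bleeds go to adjudication (Section 6), so the bleeding data should already exist. INR may be incomplete, because Table 17.1 lists post-randomization INR only for subjects on SOC. The downside is that a few bleeds that preceded edoxaban may appear in the edoxaban column of the supplementary table.
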